**Date**

## **1. Background:**

Breast reconstruction after mastectomy has been shown to provide psychosocial benefits to breast cancer patients and is considered an integral part of breast cancer treatment [1]. In general, breast reconstruction can be accomplished using the patient's own tissues (autologous), or implantable prosthetic devices (alloplastic reconstruction or breast implants). Over the last decade, there has been a significant increase in the rate of alloplastic reconstructions compared with autologous tissue reconstructions in North America [1-3].

Acellular dermal matrix (ADM) has been increasingly used in alloplastic reconstruction. ADMs are biological materials, typically of human, bovine, or porcine origin [3-6]. The tissue is processed to remove cells as well as any antigenic component to prevent immune reaction, resulting in a residual collagen matrix or scaffold that facilitates tissue ingrowth and revascularization by the host following implantation. Originally described for the use in resurfacing of burn injuries and abdominal wall repair; ADMs are now commonly used in the field of implant-based breast reconstruction post mastectomy (Figure 1). The advantages of ADM-assisted implant reconstruction is that it provides additional tissue coverage and helps in the positioning of the implant while minimizing peri-prosthetic fibrosis (i.e. capsular contracture) [6-8], the latter being especially important for patients who receive adjuvant radiation as part of their breast cancer treatment [9]. Whereas traditional implant-based breast reconstruction occurs in a “delayed” fashion, performed at least 6 months post mastectomy; the use of ADMs have allowed conversion in the appropriate patient to a single stage, “immediate” breast reconstruction (done at the same operative procedure as the mastectomy) [3-6].

November 24, 2016

The significant impact on reduced operative procedures for the patient [6-9], psychological benefit from having restoration of the breast immediately post mastectomy (i.e. direct to implant breast reconstruction) [10-11], cost savings from sparing a second surgery [12-15] as well as improved aesthetic outcomes (compared to non-ADM assisted breast implant reconstruction) [16-17] has made the ADM-assisted approach to become a standard of care at many centers and widely adopted throughout the world [18-21]. Currently at the Ottawa Hospital, a cursory audit in 2015 demonstrated that approximately 50% of the 800 breast cancer patients underwent a mastectomy; 25% of these underwent immediate breast reconstruction for which ADM is used (i.e. around 100 breast cases per year).

Patients who undergo direct-to-implant breast reconstruction with ADMs have been found to experience similar rates of postoperative complications compared with patients who undergo two-stage reconstruction without ADMs, and therefore this procedure is generally considered to be a safe and reliable approach to breast reconstruction [18-23]. A summary of the evidence on outcomes after direct-to-implant breast reconstruction using ADMs is presented in Table 1. Overall, direct-to-implant reconstruction outcomes compare favourably with the Mentor and Allergan Core Study results, which tracked complications and revision rates following delayed two-stage implant reconstruction without ADM (24,25). On short-term follow-up, weighted analysis of the studies in [Table 1](#) shows direct-to-implant reconstruction with ADM to have lower rates of capsular contracture compared to two-stage reconstruction without ADM (0.3% versus 8.3% to 17.1%), seroma (1.2% versus 4.9%), infection (1.4% versus 3.2% to 5.7%), late revision (8.5% versus 27% to 53.3%) and implant loss (1.5% versus 5.7% to 7.7%). Higher rates of mastectomy flap necrosis in immediate reconstruction with ADM (4.7% versus 2.3%) may be

November 24, 2016

related to increased tension placed on the skin closure with immediate placement of the permanent prosthesis.

Various ADMs are offered on the market and the costs vary widely despite very similar qualities. The two most commonly used ADM products in North America by far are Dermacell and Alloderm [2-4,32]. The difference between the two products include a) the level of sterility , with Dermacell being sterilized to  $10^{-9}$  while Alloderm is sterilized to  $10^{-6}$  and b) the consistency and thickness of the biologic material and c) a significant difference in cost (standard 6x16cm piece of Dermacell = \$2200 CAD and Alloderm = \$3600 CAD). For a typical patient, the difference in cost for the hospital is about \$1400. Supporters of Dermacell advocate for its lower cost and increased sterility; whether the difference in sterility translates into a clinical difference in infection rate is unclear (standard procedure is to sterilize to  $10^{-6}$  for operative devices) [32-36]. Supporters of Alloderm advocate based on its longer term data on safety and effectiveness (2-4,19,32] as it is the ADM that has been around the longest. Each product has shown to be safe and effective (32-26). As such there exists clinical equipoise. Currently, the selection of ADM is based on non-clinical idiosyncratic decision making factors, such as the hospital's previous relationship with the vendors and preference of the surgeon. Both products are equally available to Canadian hospitals and currently at the Ottawa Hospital the product used is dependent on surgeon preference.

## **1.1 The REaCT Program**

New cancer treatments are developed through occurrence of randomized clinical trials (RCTs), comparing with either a placebo or an established treatment. Pharmaceutical company funded

November 24, 2016

trials establish the new treatments as being; better, worse or more commonly equivalent to established therapies. As a result, in clinical practice, physicians may be faced with multiple funded “standards of care”. However, comparative standard of care treatment trials are rarely conducted. One of the major barriers is expense. It is incredibly expensive to perform clinical trials as their regulatory oversight (patient consent, REB submission, contracts, drug costs, research coordination and management, data collection of multiple often superfluous endpoints, analysis) has been designed around trials of new agents or established agents for new indications.

As physicians do not know what the “best” treatment for patients is, genuine uncertainty (“clinical equipoise”) exists. In the light of different strategies chosen by investigators between those two trials aforementioned, physicians will choose between different “standards” in their personal practice, using idiosyncratic decision making processes, without the physician or the patient knowing the optimal option. Determining the optimal treatment remains an important medical issue for both patients and physicians.

This study will use an established methodology to allow comparisons of established standard of care treatment using the “integrated consent model” as part of a pragmatic clinical trial. By integrating medical and clinical practices, physicians will be able to inform their patients about the RCT, through a typical conversation between the physician and patient, without written informed consent. This clinical interaction would then be documented, as ordinarily done in practice.

Pragmatic clinical trials are being given increased importance, as they commonly consist of comparative effectiveness research, thus comparing the safety and effectiveness of diagnostic, therapeutic or delivery systems. Additionally, these studies have not only the ability to leverage patient data from electronic health records to increase sample size of trials at much lower costs,

November 24, 2016

but also enabling major national and international initiatives to generate the data needed to improve care. As such, the Integrated Consent Model is being increasingly used internationally to improve patient care. In fact, the Ottawa Hospital Cancer Centre is leading this program with over 150 patients already enrolled on REACT trials at four Canadian Cancer Centres (Ottawa, Kingston, Edmonton, Kitchener). These studies have shown excellent patient feedback with 97% of patients rating being ‘completely satisfied’ with the REACT process.

Thus, we propose a pragmatic clinical trial to evaluate AlloDerm with Dermacell in a head to head randomized fashion, with regards to the postoperative complications, namely infection, seroma formation (as measure by drain duration and output), loss of the implant, incidence of revisional surgery and capsular contracture. These postoperative sequelae have significant implications to the patient, surgeon and health care system. The most significant of these are postoperative infection, which can result in prolonged antibiotic use, hospital admission, loss of implant, and delay in adjuvant breast cancer therapy.

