## 5. Outcomes

Primary outcome: Postoperative duration of drain placement (days)

Secondary outcomes: All outcomes are measured within 6 months of the initial surgery

- Episodes of seroma formation requiring aspiration

November 24, 2016

- Loss of implant
- Revisional surgery/ return to operating room
- Wound dehiscence or debridement
- Capsular contracture (as identified by the plastic surgeon)
- Number of additional postoperative clinic visits with the plastic surgeon (beyond the routine)
- Economic impact will be assessed based on calculation of total costs with each material used to include the material costs, duration of operative room use, clinic and inpatient hospital costs, surgical billing costs and anaesthesia costs

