## **6. Study Procedures**

All patients undergoing mastectomy for breast cancer or breast cancer prophylaxis are seen at the WBHC at the Ottawa Hospital. Patients eligible and consenting for immediate breast reconstruction with an implant will be introduced to the REACT-ADM study and a standardized verbal consent for randomization will be recorded in the clinic notes. The clinical research assistant (CRA) will be performing the randomization and will inform the surgeon on the day of surgery with regards to the randomization arm immediately before the surgery. Both Dermacell and AlloDerm will be readily available in the operating room for use in case of randomization into either arm.

The plastic surgeon will be informed of the randomization arm and will proceed with the surgery in the usual fashion, with standard, equivalent procedures used for both (aseptic technique, drainsplacement, oral antibiotics for 1 week postoperatively). The routine schedule of postoperative follow-up of these patients is as follows:

November 24, 2016

Breast Surgeon:

- 2 weeks
- 6 months

Plastic Surgeon:

- 1 weeks
- 2 weeks
- 6 months

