## **7. Sample size calculation and Data Analysis Plan**

The primary endpoint of the study is drain duration (days). Mean postoperative duration of drain placement is 10 days. As per informal discussion with the plastic and breast surgeons, a minimum of 4 days in drain duration between the 2 arms will be considered clinically significant. We are hypothesizing that there will be minimum of 4 day difference in drain duration, in favour of Dermacell as this is a superiority trial. As such, we will require 50 patients total (25 per arm) to demonstrate a 4 day difference in drainage duration (14 vs 10) with a standard deviation of 5. Allowing for a 10% study drop out rate, we will require a total of 56 pts or 28 patients per arm. The Ottawa Hospital currently performs 100 immediate breast reconstructions per year with ADM. As such, the study duration would be expected to be 1 years. Data will be analysed at the end of the year.

November 24, 2016

The primary endpoint of the study is drain duration (days). We will compare mean postoperative duration of drain placement between both arms by calculating the post-randomization absolute mean difference in durations and its 95% confidence interval. We will also present the associated two-sample t-statistic. If data are not normally distributed, we will compare groups using a Mann-Whitney test. Our dichotomous secondary outcomes (episodes of seroma formation requiring aspiration, loss of implant, revisional surgery/ return to operating room, wound dehiscence or debridement, capsular contracture (as identified by the plastic surgeon) will be analyzed by calculating relative risk ratios and their 95% confidence intervals. Our continuous outcome (number of additional postoperative clinic visits with the plastic surgeon beyond the routine) will be analyzed using parametric (t-statistic) or non-parametric (Mann-Whitney) tests depending on distribution of occurrences. Patients having bilateral mastectomy will have each breast evaluated separately, as 2 entries the final results database. Both breasts of the same patient will receive the same randomization arm.

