## **8. Data Collection**

Once the patient has been randomized, the study CRA will collect participant information via electronic health records. From a study standpoint only the CRA will access this information. Data not available at the time of visit will be collected from the dictated physician/surgeon note. At the time of randomization the software will also generate a reminder email to the patient's physician to collect study related data. Patients having bilateral mastectomy will have each breast evaluated separately, as 2 entries the final results database. However, both breasts of the same patient will receive the same randomization arm.

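### Must drain output be added as an outcome because Section 1.1 names it beside drain duration?

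*Combined protocol and SAP*

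**What the plan says.** Section 1.1, which is background, lists the complications the trial will compare and describes one of them as "seroma formation (as measure by drain duration and output". This is the only mention of output in the document.

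Section 5 states: "Primary outcome: Postoperative duration of drain placement (days". Its seroma item among the secondary outcomes is "Episodes of seroma formation requiring aspiration", with no volume. Section 7 bases the sample size on duration and compares duration between arms by a mean difference with a 95% confidence interval. It gives relative risks for the dichotomous secondary outcomes, aspirated seroma included, and has no analysis of output.

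Section 6 says: "The plastic surgeon will be informed of the randomization arm and will proceed with the surgery in the usual fashion". It describes the same usual procedures for both arms. It mentions placing drains, but not who removes them or on what basis.

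Section 8 says that "the study CRA will collect participant information via electronic health records". It contains no list of variables.

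**The concern.** The document names two measures of seroma and carries only one into the outcomes, the analysis and the data collection. Taken alone, that could be an outcome lost between the rationale and the plan.

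The lost measure also seems to be the one that would help most in reading the primary result. Drain duration depends on how much fluid drains and on when someone takes the drain out. At least one surgeon knows the arm, no blinding of anyone is described, and Section 3 predicts an advantage for Dermacell. If removal timing differed by arm for reasons other than drainage, a difference in duration could appear or be hidden. A volume not recorded during care could not be recovered afterwards, so the time to ask for it would be before data collection.

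**Working it through.** **1. Sections side by side.**

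| Section | Drain duration | Drain output |
|---|---|---|
| 1.1 Background | named | named |
| 5 Outcomes | sole primary outcome | absent |
| 6 Procedures | placement only | absent |
| 7 Sample size and analysis | sample size and primary analysis | absent |
| 8 Data collection | not named | not named |

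The two operative sections, 5 and 7, agree. Section 8 is weak evidence of an omission, because it does not name the primary outcome either.

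**2. The stated sample size.** Section 7 gives a difference of 4 days, SD 5, 25 per arm and 10% dropout. Alpha and power are not stated; I assume two-sided 5% and 80%.

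- n per arm = 2 × (1.960 + 0.842)² × 5² / 4² = 2 × 7.85 × 1.5625 = 24.5, so 25 per arm and 50 in total.
- 50 / (1 − 0.10) = 55.6, so 56 in total, or 28 per arm.

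Both figures reproduce from duration alone. The document gives no mean, SD or target difference for output.

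**3. What a shift in removal timing could do, and whether output enters.** The shifts here are assumed; none comes from the document. Take 25 independent patients per arm, so SE = 5 × √(2/25) = 1.414 days, with critical t on 48 df = 2.011. The chance of p < 0.05 follows from a noncentral t with noncentrality (net difference) / 1.414.

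| True product difference | Removal shift | Net difference | Chance of p < 0.05 |
|---|---|---|---|
| 0 | 0 | 0 | 5.0% |
| 0 | 0.5 day | 0.5 | 6.4% |
| 0 | 1 day | 1 | 10.7% |
| 0 | 2 days | 2 | 28.3% |
| 4 days | none | 4 | 79.2% |
| 4 days | 1 day, opposing | 3 | 54.7% |
| 4 days | 2 days, opposing | 2 | 28.3% |

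These rates depend on the assumed shift, the SD and n. Output appears in none of them, so recording it would leave every row as it is. They describe a hazard of any duration endpoint and do not measure the cost of omitting output. Section 7 also enters each breast of a bilateral patient separately ("Patients having bilateral mastectomy will have each breast evaluated separately, as 2 entries the final results database"). The effect of that on error rates is a separate clustering question.

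**4. What an output comparison would deliver.** With one value per patient, the 95% half-width is t × √(2/n) in SD units.

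| Patients per arm with a volume | Half-width | Difference needed for 80% power |
|---|---|---|
| 25 | 2.011 × √(2/25) = 0.57 SD | 0.81 SD |
| 20 | 0.64 SD | 0.91 SD |
| 15 | 0.75 SD | 1.06 SD |

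Only a large difference would be seen, and missing volumes make this worse.

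**5. What a result would mean.** The last 24-hour volume is fixed by the removal decision itself. If removal follows a volume threshold, which the document neither states nor denies, that volume will be similar in the two arms by construction. Total volume accumulates until removal, so it carries the removal time within it. A difference between arms could reflect removal timing or drainage caused by the product. No difference would not exclude differential removal.

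**The case for a change.** The best case for adding output is that it is the protocol's own second measure, it is cheap, and it is lost if not recorded. The other seroma evidence will be thin. The weighted seroma rate in Table 1 is 6/505 = 1.2%. Applied to 50 patients with one breast each, that is 50 × 0.012 = 0.6 expected events, too few to support or contradict a duration result. One added field leaves the sample size unchanged.

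Much of this stands. The mismatch is real, the surgeon knows the arm, no basis for removal is described, and aspirated seromas will probably be few.

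What does not stand is the step to a needed change:

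- Calling the trial open-label with an unblinded removal decision is inference. The document does not say who decides removal, and nothing in it shows bias.
- The added measure would not resolve the worry, for the reasons in steps 4 and 5 of the working.
- It is not clearly cheap. The document does not show that charts hold volumes, so clinicians might have to record them prospectively. Section 8 says "the software will also generate a reminder email", but this happens at randomization, before any drain is removed, so it is poorly timed to capture a volume at removal. The number of drains per breast is not given, so a single last volume per breast is not defined.
- Section 1.1 counts "data collection of multiple often superfluous endpoints" among the burdens that make trials expensive. Leaving out an ambiguous measure is consistent with that pragmatic aim.
- If charts do hold volumes, the record review can still retrieve them, and nothing in the plan prevents a descriptive summary.

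**Conclusion.** No change to the plan follows. This is a clerical mismatch of two words in background text. Striking them would cure it as fully as adding an endpoint would. Following Sections 5 and 7 as written gives one primary outcome, one primary comparison and a sample size that reproduces at 25 per arm and 56 in total. None of these moves if output is dropped or kept.

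Whether to collect drain volumes is a matter of preference. At 25 patients per arm the comparison would have a half-width of about 0.57 SD, and its result would be ambiguous either way. The possibility that removal timing differs by arm belongs to the choice of duration as the endpoint; output would neither detect it reliably nor correct it.

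This conclusion rests on three readings: Sections 5 and 7 govern over Section 1.1; no volume is needed to compute or interpret the stated primary comparison; and the document does not show who decides removal or that any bias exists. The precision figures assume a two-sided 5% level and one value per patient.

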## **2. Study Aim**

The aim of this study is to evaluate the postsurgical complications of AlloDerm versus Dermacell use in immediate breast reconstruction.

November 24, 2016

### **3. Hypothesis**

We predict that Dermacell will have reduced postoperative complications as compared to Alloderm due to its improved sterility.

### **4. Consent Process**

Patients will be asked to provide oral consent to be randomized to once either Alloderm or Dermacell. In this study the investigator will obtain oral consent using the attached REB approved consent script.

If the patient agrees to participate in the study, then the surgeon will dictate in the progress note they have had the above type of conversation with the patient. There will be no need for the patient to sign an informed consent form. The patient will be given a written summary of the general information about the study as well.

### **4. Study Design**

In this randomized superiority trial, the site investigator will have the on-line program uploaded to their health authority secured computer in clinic or electronic portable device (e.g. smartphone) in order to randomize participants. The surgeon must dictate that the verbal consent and eligibility review has taken place prior to randomization.

Inclusion Criteria:

- Female patient
- Ages 20-90

November 24, 2016

- All patients undergoing mastectomy for breast cancer or prophylaxis for breast cancer with immediate implant-based reconstruction
- Able to provide verbal consent

Exclusion Criteria:

- Patients who have had prior chest wall or irradiation on the reconstructed side
- Patients not undergoing immediate breast reconstruction at the time of mastectomy
- Any patient with a contraindication to immediate breast reconstruction

It should be noted that patients who undergo bilateral mastectomy and bilateral immediate implant reconstruction should be randomized to the same type of ADM for each breast ie the randomization is at the patient level and not the breast level. Patients having bilateral mastectomy will have each breast evaluated separately, as 2 entries the final results database. Both breasts of the same patient will receive the same randomization arm.

A history of smoking, BMI > 40, and D cup breast size or grade III ptosis are all contraindications to immediate breast reconstruction as the risk of postoperative complications are significantly higher (wound infection, dehiscence, implant loss, seroma) than the average patient and thus these patients would be excluded from the study.

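### The protocol names two different people as the randomiser, and the investigator-run route can let the surgeon know the arm before the day of surgery, against the plan's own late-disclosure rule

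*Combined protocol and SAP*

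**What the plan says.** Three sections bear on how a patient is randomised.

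- **4. Study Design:** "the site investigator will have the on-line program uploaded to their health authority secured computer in clinic", or on a portable device such as a smartphone, for the purpose of randomising participants. One timing rule is attached: "The surgeon must dictate that the verbal consent and eligibility review has taken place prior to randomization".
- **6. Study Procedures:** the CRA is the one who "will be performing the randomization and will inform the surgeon on the day of surgery with regards to the randomization arm immediately before the surgery". The section adds that "Both Dermacell and AlloDerm will be readily available in the operating room for use in case of randomization into either arm", and that the surgeon "will proceed with the surgery in the usual fashion, with standard, equivalent procedures used for both".
- **8. Data Collection:** "At the time of randomization the software will also generate a reminder email" to the patient's physician, as a prompt to collect study data. It does not say whether the message names the arm.

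The Consent Process section has the investigator obtain oral consent and the surgeon dictate that the conversation took place. In practice it therefore treats the consenting investigator as the surgeon.

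**The concern.** Study Design and Study Procedures cannot both be followed on who performs the randomisation. The difference matters because only the CRA route contains a rule that keeps the arm from the surgeon until just before the operation. A surgeon-investigator who dictates consent in clinic and then randomises on a phone complies with Study Design and bypasses that rule.

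An online program may well conceal the next allocation. The exposure here is different: knowledge of the arm between randomisation and surgery. Several features of the plan make that interval sensitive:

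- The surgeon is told the arm, and the Background says product choice at the hospital currently depends on surgeon preference.
- The Hypothesis section predicts fewer complications with Dermacell.
- Under Premature withdrawal, participants may leave for any reason, and the investigator may withdraw them for reasons that include logistics.
- Eligibility includes a general exclusion for any contraindication to immediate reconstruction, which leaves room for a second judgement before surgery.
- The data analysis plan defines no analysis population, so nothing requires patients lost at this stage to be kept. A patient who leaves before surgery may also have no drain duration to analyse.

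**Working it through.** **1. The two routes side by side**

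| | Study Design | Study Procedures |
|---|---|---|
| Who randomises | Site investigator | CRA |
| Earliest time | After consent and eligibility are dictated | Not stated |
| When the surgeon learns the arm | Not stated; at once if the surgeon is the investigator | Day of surgery, immediately before it |

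Study Procedures has consent recorded in the clinic notes, so the one precondition in Study Design can be met at the clinic visit. Nothing in Study Design delays randomisation beyond that point, and nothing requires it to happen then.

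**2. The plan's sample size**

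Inputs from section 7: difference 4 days, SD 5, 25 per arm, 10% drop-out, 28 per arm. Alpha and power are not stated; I assume 5% two-sided and 80%.

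n per arm = 2 × (1.960 + 0.842)² × 5² / 4² = 24.5, rounded up to 25. Then 25 / 0.9 = 27.8, rounded up to 28. The plan's figures are reproduced, and settling the randomisation route leaves them unchanged.

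**3. What selective loss before surgery could do**

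The documents give no rate of such loss, so this is an illustration. Assumptions: normal durations with SD 5, no true difference, 28 per arm, and k = 2 or 3 patients lost, all from one arm and all at the long-duration end. The allowance of 28 − 25 = 3 per arm makes k = 3 consistent with the plan's own drop-out figure.

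If the leavers average m days above their arm's expected mean, the mean of those who stay falls by k × m / (28 − k).

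*Perfect foresight (the k longest durations leave).* The top 2 of 28 normal values average 1.80 SD, or 9.0 days above the mean; the top 3 average 1.64 SD, or 8.2 days.

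- k = 2: 2 × 9.0 / 26 = 0.69 days, and 0.69 / 4 = 17% of the target difference.
- k = 3: 3 × 8.2 / 25 = 0.98 days, and 0.98 / 4 = 25% of the target difference.

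*Imperfect foresight.* The losses would occur before any drain is placed, so departure can depend only on something known preoperatively. If that predictor has correlation r with drain duration, the expected shift is r times the figure above. Rejection rates of the two-sided 5% t-test are from simulation:

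| r (assumed) | Shift, k = 2 / k = 3 (days) | Type I error, k = 2 / k = 3 |
|---|---|---|
| 1 (perfect foresight) | 0.69 / 0.98 | about 9% / 13% |
| 0.5 | 0.34 / 0.49 | 6.0% / 6.8% |
| 0.3 | 0.20 / 0.30 | 5.3% / 5.6% |
| 0 | none | 5.0% |

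**4. Power**

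The loss of numbers alone matters little: t-test power for a 4-day difference is 84% at 28 against 28 and 81% at 28 against 25.

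**The case against.** The strongest reply is that the two sections can be read together: Study Design describes the tool supplied to the site, and Study Procedures says who operates it and when the surgeon is told. On that reading the only disclosure rule in the protocol already gives the protection sought. The reading is possible, but it has to be supplied by the reader. Study Design says the investigator holds the program in order to randomise, and does not mention the CRA. The contradiction over the randomiser therefore stands.

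Four stronger readings are tempting and are not supported.

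- *That the arm is known from the clinic visit onward.* Study Design does not say this. The reference to a clinic describes where the computer is, and a phone could be used on the day of surgery. Early knowledge is permitted, not prescribed.
- *That Data Collection adds a third conflicting rule.* The email is described only as a data-collection reminder and fits either route. Whether it shows the arm is a point to confirm.
- *That surgical planning would change with the arm.* Both products are in the operating room and procedures are to be equivalent. The documents give no basis for saying that planning would differ.
- *That the type I error would be 9% to 13%.* This needs perfect preoperative knowledge of a postoperative outcome. Even the lower figures assume that every loss falls in one arm and in the same prognostic direction.

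It is also fair to say that no section requires randomisation on the day of surgery. Study Procedures fixes only when the surgeon is told.

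**Conclusion.** The concern holds as a contradiction over who randomises, with a conditional consequence. If the Study Design route is used, the surgeon-investigator can know the arm before the day of surgery, which removes the late disclosure in Study Procedures and leaves arm-dependent withdrawal or re-judged eligibility uncontrolled.

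The size of any resulting bias cannot be measured from the documents. For 2 or 3 losses confined to one arm, type I error is about 5% to 7% at assumed correlations of 0.3 to 0.5, and the perfect-foresight figure bounds it from above. The bias would be modest against a 4-day target and would not overturn the design. The case for acting rests on the contradiction and on how cheaply it is removed; selective loss cannot be undone once patients have been randomised by mixed routes.

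**What to change.** Bring Study Design into line with the rule already in Study Procedures:

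- Remove the investigator-run clinic or smartphone route, and restrict access to the program accordingly.
- Name the CRA as the only person who randomises, after consent and eligibility are recorded.
- State that the arm is withheld from the surgical team until immediately before surgery. Randomising on the day itself is one way to achieve this but is not required.
- Confirm in Data Collection that the reminder email does not show the arm.

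The cost is protocol wording and a user-access setting. The CRA must be available to release the arm on each surgery day, which Study Procedures already assumes. The sample size stays at 50 evaluable and 56 randomised. The change does not blind the surgeon after disclosure; any effect of that on drain removal is a separate matter.
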